8.4.4 Pooled and Subgroup Analyses

Pooled and subgroup analyses will be performed, taking into consideration baseline characteristics of the patients and of the underlying disease, risks factors for clinical deterioration or death, vaccination status, duration of the infection prior to study entry, and concomitant therapies (e.g., immunomodulatory agents —including glucocorticoids—, oxygen supplementation).

Subgroup analysis of TEAEs and clinically relevant laboratory tests will be performed based on prognostic factors of medical interest.

8.5 SUMMARY OF ESTIMANDS AND STATISTICAL TESTS

The primary estimand corresponding to the primary endpoint is defined as:

Treatment: Participants will be randomised to receive plitidepsin versus control in each group.

Population: Participants as defined through the inclusion and exclusion criteria, who have been randomised to the trial and who have taken at least 1 dose of study treatment (plitidepsin or control).

Variable:

–1-month all-cause mortality rate (Day 30 since randomisation).

Intercurrent events:

–The participant's data are collected and included in the analysis without regard for treatment discontinuation (treatment-policy strategy).

–In the event of the participant initiating another non-protocol therapy, 1-month all-cause mortality rate will be evaluated regardless of initiation of new non-protocol therapy (treatment-policy strategy).

Population level summary: the posterior probability associated for the odds ratio of 1-month all-cause mortality rate from a Bayesian logistic regression for each group comparison.

Below a summary table where main/supportive analyses are described. P values except for the primary analysis have to be considered as exploratory and nominal values will be shown.

Endpoints	Analyses
Efficacy primary endpoint	
1-month all-cause mortality rate.	
 -Bayesian odds ratio (primary analysis by CHBM) -Bayesian odds ratio (Berry's Method) - Unstratified odds ratio (Univariate Logistic regression) - Stratified odds ratio (Multivariate Logistic regression)
Key secondary endpoint	
Time to confirmed negativisation in SARS-CoV-2 antigen test or RT-PCR Ct > 30.	
 -Kaplan-Meier (unstratified and stratified) -Cox regression (unstratified and stratified)
Efficacy secondary endpoints	
Time to sustained end of COVID-related hospital care from the time of randomisation. Sustained discharge is defined as no subsequent admission within 30 days of initial end of hospital care [up to day 60 (± 3)], related to either COVID-19 or COVID-19 therapy	
 -Kaplan-Meier (unstratified) -Cox regression (unstratified)
Time to sustained improvement (defined in Section 7.1.3) and resolution of selected COVID signs/symptoms (See Appendix 10 - COVID-19 signs/symptoms checklist).	
 -Kaplan-Meier (unstratified) -Cox regression (unstratified)
Distribution of patients according to their clinical status by the 11-category WHO Clinical Progression Scale, at Days 4 (± 1), 8 (± 1), 15 (± 1), 30 (± 2), and 60 (± 3) (See Appendix 1 – 11-Point World Health Organization (WHO) Clinical Progression Scale).	
 -Frequencies -Unstratified odds ratio (ordinal)

Endpoints	Analyses
Percentage of patients requiring oxygen therapy on Days 4 (± 1), 8 (± 1), 15 (± 1), 30 (± 2), and 60 (± 3).	-Frequencies -Unstratified odds ratio (ordinal)
Time to sustained discontinuation (i.e., at least 7 days) of oxygen supplementation.	-Kaplan-Meier (unstratified) -Cox regression (unstratified)
Safety secondary endpoints	
Treatment-emergent adverse events (TEAEs).	-Frequencies (severity grade by NCI-CTCAE v5)
TEAEs \geq grade 3 according to the National Cancer Institute [NCI]-Common Terminology Criteria for AEs (CTCAE v.5.0).	-Frequencies
Adverse events of special interest (AESIs).	-Frequencies (severity grade by NCI-CTCAE v5)
Serious adverse events (SAEs).	-Frequencies (severity grade by NCI-CTCAE v5)
Drug related Serious Adverse Events (i.e., SARs).	-Frequencies (severity grade by NCI-CTCAE v5)
Adverse events leading to treatment discontinuation.	-Frequencies (severity grade by NCI-CTCAE v5)
Deaths (COVID-19-related/all).	-Frequencies
Change respect to baseline in individual study-defined laboratory parameters (See Section 5.7 , 5.8 and 5.9 and Appendix 8 - Clinical Laboratory Analyses).	-Frequencies (severity grade by NCI-CTCAE v5)
Change respect to baseline in individual vital signs (See Section 5.7 , 5.8 and 5.9).	-Frequencies
Other Secondary/Exploratory Endpoints	
Percentage of patients requiring advanced oxygen support on Days 4 (± 1), 8 (± 1), 15 (± 1), 30 (± 2), and 60 (± 3).	-Frequencies -Unstratified odds ratio

Endpoints	Analyses
Time to intensification of respiratory support (WHO >5) (See Appendix 1 – 11-Point World Health Organization (WHO) Clinical Progression Scale).	-Kaplan-Meier (unstratified) -Cox regression (unstratified)
Total duration of advanced oxygen support.	-Summary statistics -U-Mann Whitney
Percentage of patients requiring high-flow oxygen on Days 4 (± 1), 8 (± 1), 15 (± 1), 30 (± 2), and 60 (± 3).	-Frequencies -Unstratified odds ratio
Total duration of high-flow oxygen therapy per patient.	-Summary statistics -U-Mann Whitney
Percentage of patients requiring non-invasive mechanical ventilation on Days 4 (± 1), 8 (± 1), 15 (± 1), 30 (± 2), and 60 (± 3).	-Frequencies -Unstratified odds ratio
Total duration of non-invasive mechanical ventilation per patient.	-Summary statistics -U-Mann Whitney
Percentage of patients requiring invasive mechanical ventilation or ECMO on Days 4 (± 1), 8 (± 1), 15 (± 1), 30 (± 2), and 60 (± 3).	-Frequencies -Unstratified odds ratio
Total duration of invasive mechanical ventilation or ECMO per patient.	-Summary statistics -U-Mann Whitney
Percentage of patients requiring admission to ICU on Days 4 (± 1), 8 (± 1), 15 (± 1), 30 (± 2), and 60 (± 3).	-Frequencies -Unstratified odds ratio
Total duration of intensive care unit (ICU) stay.	-Summary statistics -U-Mann Whitney
Time to onset of additional (i.e., not present at baseline) immune-modulating drugs.	-Kaplan-Meier (unstratified) -Cox regression (unstratified)

Endpoints	Analyses
Percentage of patients receiving immune-modulating drugs on Days 1, 4 (± 1), 8 (± 1), 15 (± 1), 30 (± 2), and 60 (± 3).	-Frequencies -Unstratified odds ratio
Time to onset of additional (i.e., not present at baseline) antiviral drugs.	-Kaplan-Meier (unstratified) -Cox regression (unstratified)
Percentage of patients receiving subsequent antiviral drugs (i.e., not present at baseline) on Days 4 (± 1), 8 (± 1), 15 (± 1), 30 (± 2), and 60 (± 3).	-Frequencies -Unstratified odds ratio
Percentage of patients with a new infection by Days 4 (± 1), 8 (± 1), 15 (± 1), 30 (± 2), and 60 (± 3).	-Frequencies -Unstratified odds ratio
Cumulative mortality (all-cause and related to COVID-19) by Days 4 (± 1), 8 (± 1), 15 (± 1), 30 (± 2), and 60 (± 3).	-Frequencies -Unstratified odds ratio
Percentage of patients in each study group who require subsequent admission within 30 days of initial end of hospital care [up to day 60(± 3)], related to either COVID-19 or COVID-19 therapy.	-Frequencies -Unstratified odds ratio
Change respect to Day 1 in the viral load of SARS-CoV-2, measured by RT-PCR, by Days 4 (± 1), 8 (± 1), 15 (± 1), 30 (± 2), and 60 (± 3), in each study group.	-Summary statistics -Univariate test (Fisher exact test or U-Mann Whitney) -Mixed model
Percentage of patients in each study group with undetectable viral load, by Days 4 (± 1), 8 (± 1), 15 (± 1), 30 (± 2), and 60 (± 3).	-Frequencies -Unstratified odds ratio
Time to either undetectable viral load of SARS-CoV-2 or > 2 logs reduction respect to Day 1.	-Kaplan-Meier (unstratified) -Cox regression (unstratified)

Endpoints	Analyses
Change respect to baseline in inflammatory biomarkers (C- reactive protein [CRP], procalcitonin, lactate dehydrogenase [LDH], ferritin, neutrophil-to-lymphocyte ratio, and multiplex cytokines assay, by Day 4 (± 1), 8 (± 1), 15 (± 1) and 30 (± 2) and 60 (± 3)).	-Univariate test (Fisher exact test or U-Mann Whitney) -Mixed model
Change respect to baseline in individual serological assessments against SARS-CoV-2, by Days 30 (± 2), and 60 (± 3).	-Univariate test (Fisher exact test or U-Mann Whitney) -Mixed model
Change respect to baseline in individual T-cell response against SARS-CoV-2 by Days 30 (± 2), and 60 (± 3).	-Univariate test (Fisher exact test or U-Mann Whitney) -Mixed model
Change respect to baseline to Days 15 (± 1), and 30 (± 2) in chest X-ray findings (Brixia score, centrally assessed) (Appendix 9 – Brixia Score).	-Univariate test (Fisher exact test or U-Mann Whitney) -Mixed model
Percentage of patients requiring modification of the therapy (drugs, dose or schedule) for the underlying disease.	-Frequencies -Unstratified odds ratio
Time in which pre-scheduled therapies for the control of the underlying disease were not able to be administered.	-Kaplan-Meier (unstratified) -Cox regression (unstratified)
Risk for mortality / clinical deterioration according to individual clinical characteristics and laboratory observations present at baseline, scores of validated scales (e.g., ISARIC-4C), as well as features related to COVID-19 [including SARS-CoV-2 variant (if available), vaccination status, duration of the infection, and inflammation-related parameters [neutrophil-to-lymphocyte ratio (NLR), protein C reactive, interleukine-6 (IL-6) and lymphocytes], the underlying disease, and other co-morbidities.	-Frequencies -Unstratified odds ratio
Limited-sampling pharmacokinetics assessment (See Section 7.6).	

Endpoints	Analyses
PK-PD analysis.	

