Clinical evaluation	
 COVID-19-related signs and symptoms checklist (Appendix 10 - COVID-19 signs/symptoms checklist) and need for hospitalisation. Complete physical examination. Height in centimetres (cm) will be measured at screening. Body weight will be measured in kilograms (kg). Body mass index will be calculated. A full physical examination will be performed and should include general appearance, skin, neck, eyes, throat, lungs, heart, abdomen, back, lymph nodes, extremities, and neurological examinations, including Glasgow score (See Appendix 11 – Glasgow Coma Scale). Clinical status (11-point WHO Clinical Progression Scale) Vital signs will include body temperature (°C), SBP (mmHg), DBP (mmHg), pulse rate (bpm) and respiratory rate (breaths/min). Lung function tests include partial pressure of oxygen (PaO₂), fraction of inspired oxygen (FiO₂) and oxygen saturation (SpO₂). PaO₂/FiO₂ ratio will also be measured; either Ellis or Rice formulae can be used to estimate PaO₂/FiO₂ ratio (Appendix 5 - Imputation of PaO₂/FiO₂ ratio).
Detection of SARS-CoV-2	
 qRT-PCR SARS-CoV-2 or SARS-CoV-2 Rapid Antigen Test (RAT) 
Documented diagnosis of SARS-CoV-2 infection, determined by a regulatory approved test, collected no more than 3 days prior to study randomisation, with either a Ct value ≤30 or a positive antigen test.
 
SARS-CoV-2 variant will be documented at any time during the study, if available information exists.

Minimum set of laboratory tests for screening (at site's laboratory)	
Haematology: differential white blood cells (WBC) counts (including neutrophil and lymphocyte counts), platelet count (See Appendix 8 – Clinical Laboratory Analyses).
 
Biochemistry: Liver function test (ALT, total bilirubin (direct bilirubin if total is abnormally elevated), calculated CrCL [as per Chronic Kidney Disease Epidemiology Collaboration (CKD-

	PROCEDURES / ASSESSMENTS
	EPI)], C-reactive protein (CRP), blood urea nitrogen (BUN)/urea (See Appendix 8 – Clinical Laboratory Analyses).
ECG	A 12-lead ECG will be performed in triplicate. Cardiac rhythm will be identified in ECG intervals of at least 30 seconds of duration. PR interval, QT interval (raw and QTcF), heart rate and QRS complex, with specialist assessment/judgment of further evaluation if appropriate.

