5.7 EVALUATIONS AND PROCEDURES DURING TREATMENT

	ASSESSMENT/PROCEDURES	TIME
Clinical evaluation	
 COVID-19-related signs and symptoms checklist (Appendix 10 – COVID-19 signs/symptoms checklist). Clinical status (11-point WHO Clinical Progression Scale). Vital signs will include body temperature (°C), SBP (mmHg), DBP (mmHg), pulse rate (bpm) and respiratory rate (breaths/min). Targeted physical examination. A targeted physical examination will include heart, lungs, abdomen, extremities plus central nervous system (CNS) assessment, based on the investigator's decision as per clinical evolution. Lung function tests include PaO₂, FiO₂ and SpO₂. PaO₂/FiO₂ ratio will also be measured; either Ellis or Rice formulae can be used to estimate PaO₂/FiO₂ ratio (Appendix 5 - Imputation of PaO₂/FiO₂ ratio). 	Days 1, 2, 3, 4 (± 1). When applicable, these assessments should be performed before treatment administration.

	ASSESSMENT/PROCEDURES	TIME
	
 • Concomitant therapies. • Subsequent medications for SARS-CoV-2 infection. • Subsequent medications for the underlying disease. 	Days 1, 2, 3, 4.
Laboratory tests*	Haematology: haematocrit, red blood cells (RBC), differential WBC counts (including neutrophil and lymphocyte counts), platelet count and haemoglobin (See Appendix 8 – Clinical Laboratory Analyses).	Days 1, 4 (± 1), and whenever clinically indicated for an AE evaluation. When applicable, these assessments should be performed before treatment administration.
	Biochemistry: Liver function test [ALT, AP, AST [†] , albumin, total bilirubin (direct bilirubin if total is abnormally elevated)], lactate dehydrogenase (LDH), glucose [fasting], sodium, potassium, calcium, BUN/urea, gamma glutamyl transferase (GGT), creatinine, calculated creatine clearance [CKD-EPI], creatine phosphokinase (CPK), amylase, lipase, procalcitonin, ferritin, and CRP (See Appendix 8 – Clinical Laboratory Analyses).	Days 1, 4 (± 1), and whenever clinically indicated for an AE evaluation. When applicable, these assessments should be performed before treatment administration.
	Coagulation: D-Dimer (See Appendix 8 – Clinical Laboratory Analyses).	Day 1, 4 (± 1), and whenever clinically indicated for AE evaluation. When applicable, these assessments should be performed before treatment administration.
	Urine analysis (semi-quantitative elemental tests	Day 1 (previous to treatment administration). Repeat whenever

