7.1.3 Clinical Status

Clinical status (including the need for oxygen supplementation) will be assessed at least once a day, or whenever it changes, while receiving hospital care and on Days 4 (± 1 day), 8 (± 1 day), 15 (± 1 day), 30 (± 2 days), 45 (± 2 days) and 60 (± 3 days), using the 11-point WHO Clinical Progression Scale ([Appendix 1 – 11-Point World Health Organization \(WHO\) Clinical Progression Scale](#)).

COVID-19 signs or symptoms will be systematically collected and scored according to a check list ([Appendix 10 - COVID-19 signs/symptoms checklist](#)) together with the WHO Clinical Status. Research team will record a daily severity rating of their symptom severity over the past 24 hours based on NCI-CTCAE v5.0 criteria. Sense of smell and sense of taste will each be rated on a 3-point Likert scale where: “0” is reported if the sense of smell/taste was the same as usual, “1” if the sense of smell/taste was less than usual, and “2” for no sense of smell/taste.

Sustained improvement of all targeted COVID-19 signs/symptoms is defined as the event occurring on the first of 4 consecutive days when all symptoms scored as NCI-CTCAE category of moderate-severe intensity, or requiring medical intervention, or limiting instrumental ADL (see [Appendix 10 – COVID-19 signs/symptoms checklist](#)) are scored as mild or absent AND all symptoms scored mild or 0 (absent) at study entry are scored as 0.

The first day of the 4 consecutive-day period will be considered the First Event Date.

Sustained resolution is defined as when all targeted symptoms are scored as 0 for 4 consecutive days. The first day of the 4 consecutive-day period will be considered the First Event Date.

For any symptoms not present at baseline, it must be absent at Day 30 (+/-2) to be counted as sustained alleviation/resolution.

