8.1 SAMPLE SIZE CALCULATION

Our intention is to conduct this study with 4 groups of immunocompromised patients.

A) Randomised groups (1-3)

Patients in three of the four groups will be randomly assigned to one of two arms. Each randomised group will have a sample size of 40 patients (20 in the experimental arm, 20 in the control arm).

Given the exploratory nature of this phase II study, this sample size has been chosen based on operational considerations to allow the feasibility of accrual in this relatively small population and also provide preliminary estimates to establish an updated prior distribution of the mortality rates for further investigation using Bayesian methods in a potential Phase III study.

The operating characteristics of the calibrated Bayesian hierarchical model (CBHM) described by Chu and Yuan (93) have been investigated by means of the CBHM package from Yuan at MD Anderson Cancer Center (94), and with reference to the JAGS program running in R version 4.2.1 (95) on Microsoft Windows 10.

Within the CBHM simulations, 5000 Markov-chain Monte Carlo (MCMC) repetitions per scenario were simulated with a range of operating characteristics for the null, alternative and true mortality rates moving from 5% to 95% in steps of 5% ([Table 4](#)). A maximum sample size of 40 per randomised group was set through the CBHM simulations, which in turn determines whether there is a need for the total sample size to be allocated. Within all simulations, the full 120 patients were used, suggesting that this is the minimum sample size that enables decision-making. As an example, if the mortality rate in each group is 20% and we target a clinically meaningful reduction of 12.5% in the experimental arm ($H_0=20\%$, $H_1=7.5\%$), and the assumed true mortality rate is 7.5%, the simulation demonstrates that a sample size of 40 per basket will allow for a posterior probability around 0.9 in each basket (i.e. 90% probability that the

experimental arm is better than the control in each basket), ranging from 0.87 (when the data from the fastest basket is analysed) to 0.915 (at the end of the accrual of the last basket) (type I error rate= 0.05).

Table 4 Example of simulated posterior probabilities for sample size definition.

Mortality rate – control arm (null)	Mortality rate – experimental arm (alternative)	True mortality rate	Sample size per basket	Posterior probability 1st basket	Posterior probability 2nd basket	Posterior probability 3rd basket

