11.2 Demographic and Baseline Characteristics

Baseline data such as for example demographics, medical history, clinical evaluation will be described in the FAS population.

For pre-treatment characteristics with multiple measurements per patient before the start of treatment (e.g. laboratory assessments, vital signs), the baseline measurement will be considered the last value prior to or on the first day of treatment. Continuous variables that will be also presented as categorized summaries.

Age at informed consent will be summarized as continuous variable and categorized as <65y, >=65-74y and >=75y. Gender, race, stratification factors from eCRF randomization forms and from their corresponding eCRF forms, physical examination form including height, weight, BMI and abnormal results, respiratory assessments form including oxygen therapy status, SpO2, FiO2, SpO2/FiO2, PaO2 and PaO2/FiO2, vital signs form including systolic blood pressure, diastolic blood pressure, pulse and respiratory rate, ECG Test Results - Local Reading form including heart rate, PR interval, QRS duration, QT interval, QTcF interval (Fridericia's formula) and QTcF (ECG measurements will be taken in triplicates but average values will be shown by visit), SARS-CoV-2 Test, COVID 19 Vaccination, duration of the infection prior to study entry defined as time from currently COVID-19 episode diagnosis date to randomization as continuous variable and categorized as <5 days and >=5 days and any additional variable considered as clinically relevant.

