11.8 Summary of Statistical Tests

All the main characteristics for estimands to fulfill study objectives will be defined as footnotes in each table following a similar structure than primary estimand definition. Below it can be found the endpoints to measure the variable definition and the analysis method to be used. Treatment attribute is maintained as 'participants will be randomised to receive plitidepsin versus control in each group' whereas applicable and sensitivity analyses according populations defined in 8.5 will be calculated. For intercurrent events, while applicable, a treatment-policy strategy as defined for the primary estimand will be followed.

Table 3 Summary of statistical tests

Endpoints	Analyses	Population
Efficacy primary endpoint		
1-month all-cause mortality rate.	-Frequencies	-FAS population
Key secondary endpoint		
Time to confirmed negativisation in SARS-CoV-2 antigen test or RT-PCR Ct > 30.	-Kaplan-Meier (unstratified)	-FAS population

Endpoints	Analyses	Population
Efficacy secondary endpoints		
Time to sustained end of COVID-related hospital care from the time of randomisation. Sustained discharge is defined as no subsequent admission within 30 days of initial end of hospital care [up to day 60 (± 3)], related to either COVID-19 or COVID-19 therapy	-Kaplan-Meier (unstratified)	-FAS population
Time to sustained improvement (defined in Protocol Section 7.1.3) and resolution of selected COVID signs/symptoms (See Protocol Appendix 10 - COVID-19 signs/symptoms checklist).	-Kaplan-Meier (unstratified)	-FAS population
Distribution of patients according to their clinical status by the 11-category WHO Clinical Progression Scale, at Days 4 (± 1), 8 (± 1), 15 (± 1), 30 (± 2), and 60 (± 3) (See Protocol Appendix 1 – 11-Point World Health Organization (WHO) Clinical Progression Scale).	-Frequencies	-FAS population
Percentage of patients requiring oxygen therapy on Days 4 (± 1), 8 (± 1), 15 (± 1), 30 (± 2), and 60 (± 3).	-Frequencies	-FAS population
Time to sustained discontinuation (i.e., at least 7 days) of oxygen supplementation.	-Kaplan-Meier (unstratified)	-FAS population
Safety secondary endpoints		
Treatment-emergent adverse events (TEAEs).	-Frequencies (severity grade by NCI-CTCAE v5)	-As treated population
TEAEs \geq grade 3 according to the National Cancer Institute	-Frequencies	-As treated population

Endpoints	Analyses	Population
[NCI]-Common Terminology Criteria for AEs (CTCAE v.5.0).		

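### Later WHO clinical status and oxygen need are compared without the recorded baseline value, which costs precision and leaves chance baseline imbalance uncorrected

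*Protocol*

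**What the plan says.** Baseline values exist for both endpoints. Protocol 5.5.1 lists "Clinical status (11-point WHO Clinical Progression Scale)" among the screening assessments. Protocol 5.7 repeats it on Day 1 and adds: "When applicable, these assessments should be performed before treatment administration". Oxygen need belongs to the same assessment (Protocol 7.1.3: "Clinical status (including the need for oxygen supplementation) will be assessed at least once a day"), and SAP 11.2 names the "respiratory assessments form including oxygen therapy status" as a source of baseline characteristics.

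In Protocol 8.5 the rows for WHO status and for the percentage requiring oxygen carry the same two entries: frequencies and "Unstratified odds ratio (ordinal)". Neither has a baseline covariate or a stratified version. Elsewhere in that table, mortality has a stratified odds ratio and viral clearance has stratified Kaplan-Meier and Cox analyses. Viral load, inflammatory markers and the Brixia score are analysed as change from Day 1 or baseline, with a mixed model.

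Protocol 5.6 stratifies randomisation by ISARIC-4C mortality score (below 9, or 9 and above) and by graft type or underlying disease. It does not stratify by WHO or oxygen status. On size, Protocol 8.1 says: "Each randomised group will have a sample size of 40 patients (20 in the experimental arm, 20 in the control arm)".

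SAP v3.0 was written after early closure. Section 6.0 drops formal significance tests but expects the descriptive tables to support a numerical comparison of the arms. Table 3 in SAP 11.8 reduces "Distribution of patients according to their clinical status by the 11-category WHO Clinical Progression Scale", and oxygen need, to frequencies in the FAS. SAP 11.9 adds a by-visit summary of oxygen status and its change from baseline, in the as-treated population.

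**The concern.** Patients enter at very different severities. Hospital care can mean a day hospital (Protocol 4.1). Exclusion starts only at intubation, ECMO, severe ARDS, shock or multi-organ failure (Protocol 4.2). The protocol's own earlier data suggest that starting severity is prognostic: in APLICOV-PC, Day 15 discharge was 100%, 96% and 53% for mild, moderate and severe disease at baseline (Protocol 1.2.1.3.1).

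An analysis that leaves out a strong, already measured predictor gives a noisier treatment comparison. With about 20 patients per arm, a chance difference in starting oxygen need can also reappear as an apparent difference in Day 4 to Day 15 status, and the planned analysis has no means of separating the two. The ISARIC stratum used in randomisation is also absent from these two comparisons.

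**Working it through.** **Figure to reproduce.** There is none. No power or effect size is stated for these endpoints. Protocol 8.1 says of the group size that "this sample size has been chosen based on operational considerations", and its Table 4 concerns mortality.

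**Step 1: chance imbalance in baseline oxygen.** Inputs: p = 0.485 on oxygen (compassionate-use series, Protocol 1.2.1.3.3) and n = 20 per arm (Protocol 8.1). Oxygen is treated as unrelated to the ISARIC stratum.

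- SD of the between-arm difference = √(2p(1−p)/n) = √(2 × 0.485 × 0.515 / 20) = √(0.49955/20) = 0.158, or 15.8 points.
- Exact probability that two independent binomial arms differ by at least 20 points (4 patients of 20): 0.27.
- Three groups pooled, 60 per arm: SD = √(0.49955/60) = 0.091; probability of at least 20 points (12 of 60): 0.035.
- An assumed 10 per arm, as an illustration of early closure: SD = √(0.49955/10) = 0.22; probability about 0.50.

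**Step 2: is the unadjusted comparison biased?** A simulation used 4,000 trials per setting, two-sided 5%. The outcome had six ordered levels from a latent logistic model with a common odds ratio, and the baseline had four levels. A rank test was run without and with the baseline rank as covariate, standing in for the ordinal model. At 20 per arm and odds ratio 2, the mean treatment effect on ranks was −4.4 without adjustment and −4.4 with it. Type I error was 0.046 to 0.060 unadjusted and 0.045 to 0.056 adjusted. There is no sign of bias.

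**Step 3: precision.** The odds ratios and correlations are assumptions, because the documents give neither.

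| Per arm | Odds ratio | Correlation | Power unadjusted | Power adjusted | Gain (points) |
|---|---|---|---|---|---|
| 20 | 2 | 0.3 | 0.228 | 0.239 | 1.1 |
| 20 | 2 | 0.5 | 0.238 | 0.277 | 3.9 |
| 20 | 2 | 0.7 | 0.232 | 0.336 | 10.4 |
| 20 | 3 | 0.3 | 0.469 | 0.481 | 1.2 |
| 20 | 3 | 0.5 | 0.478 | 0.559 | 8.1 |
| 20 | 3 | 0.7 | 0.484 | 0.670 | 18.6 |
| 60 | 2 | 0.3 | 0.566 | 0.590 | 2.4 |
| 60 | 2 | 0.5 | 0.559 | 0.646 | 8.7 |
| 60 | 2 | 0.7 | 0.559 | 0.777 | 21.8 |

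The variance of the treatment estimate falls by about 3–7%, 15–18% and 34–41% for correlations of 0.3, 0.5 and 0.7. The Monte Carlo standard error of one power value near 0.5 is √(0.5 × 0.5 / 4000) = 0.008, so a gain of about 1 point is close to nothing.

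**Step 4: what SAP v3.0 leaves uncovered.**

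- WHO status: FAS frequencies at Days 4 to 60 (Table 3). SAP 11.2 does not name the scale, although its general mention of clinical evaluation may include it. SAP 11.9 does not name it either.
- Oxygen need: FAS frequencies at Days 4 to 60. Baseline oxygen status is described in the FAS (SAP 11.2). Change from baseline is summarised only in the as-treated population (SAP 11.9).
- Subgroup outputs, which in Protocol 8.4.4 would have considered oxygen supplementation, are cancelled (SAP 11.10).

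No specified FAS table therefore shows either endpoint against the patient's own starting point.

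**The case against.** The strongest reply is that the quoted odds ratio will no longer be fitted. SAP v3.0 has no tests, so an argument about power cannot touch the abbreviated report. That is right, and the power figures apply only to the analysis in Protocol 8.5.

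Second, a reader might infer that the unadjusted comparison confounds severity with treatment. The documents do not support that. Allocation is randomised 1:1, so the unadjusted odds ratio is a valid marginal comparison, and Step 2 agrees. An unadjusted odds ratio does lie nearer 1 than an adjusted one, but that is the difference between a marginal and a conditional quantity, not an error. Stratifying on ISARIC-4C also balances a baseline risk score; to the extent that it tracks oxygen need, the 0.27 is too high.

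Third, a reader might infer that SAP v3.0 ignores baseline oxygen altogether. It does not: SAP 11.2 and 11.9 cover part of it, and SAP 11.0 adds figures of oxygen needs over time and listings of all CRF variables. The gap for oxygen is only the FAS change table.

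Fourth, these are exploratory secondary endpoints with nominal P values, and the 65% decision rule concerns mortality. The gain is also negligible at a correlation of 0.3, and baseline may predict less at late visits, since 82% of APLICOV-PC patients were discharged by Day 15. A full 11-by-11 table would be mostly empty. All of this stands. It limits the stakes and shapes the fix, but does not explain why a recorded baseline value goes unused.

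**Conclusion.** The point holds as one of precision and chance imbalance, not bias. Protocol 8.5 omits a baseline value that is already collected for both endpoints, while giving mortality and viral clearance stratified versions in the same table.

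At 20 per arm, a baseline oxygen difference of 20 points or more has probability about 0.27, assuming 48.5% on oxygen and no relation to ISARIC stratum. The precision gain from adjustment depends on the unknown correlation: negligible at 0.3 with 20 per arm, and material from about 0.5 upward. The APLICOV-PC discharge rates make some association likely but do not fix its size.

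For SAP v3.0 the conclusion is narrower. WHO status, and oxygen need in the FAS, lack a specified display against baseline, although the tables are meant to let readers compare the arms numerically.

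**What to change.** **Protocol 8.5.** Use a proportional-odds model for WHO status and a logistic model for oxygen need, each with baseline status and the ISARIC stratum as covariates. Keep the covariates to few at 20 per arm. The downside is small: the odds ratio becomes conditional on those covariates, and the models may be sparse in small groups.

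**SAP v3.0, Table 3.** In the FAS, show baseline WHO status beside each visit, and tabulate improved, unchanged or worsened from baseline by arm, using collapsed categories. Produce the oxygen change-from-baseline summary of SAP 11.9 for the FAS as well.

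**Cost.** SAP wording, a few table shells and one or two model terms. No new data are needed.
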